## PROTOCOL SYNOPSIS

Protocol Number:	DS5565-A-J313
Investigational Product:	DS-5565
Active Ingredient(s)/INN:	Mirogabalin
Study Title:	A Japanese, phase 3, open-label, 14-week study of DS-5565 in patients with pain associated with diabetic peripheral neuropathy (DPNP) with renal impairment or post-herpetic neuralgia (PHN) with renal impairment
Study Phase:	Phase 3
Indication Under Investigation:	DPNP or PHN
Study Objectives:	
Primary objective: To characterise the safety and tolerability of DS-5565 in subjects with moderate to severe renal impairment
 
Secondary objectives:
 

• To evaluate the effect of DS-5565 on the Average Daily Pain Score (ADPS)

• To evaluate the ADPS responder rate (the proportion of subjects with <math>\geq 30\%</math> and <math>\geq 50\%</math> reduction from baseline to Week 14)

• To evaluate the effect of DS-5565 on pain questionnaire, using the Short-Form McGill Pain Questionnaire ([SF-MPQ]: sensory, affective and total subscales, Visual Analog Scale, and present pain intensity)

• To assess the effect of DS-5565 on sleep and patient impressions in pain

• To evaluate pharmacokinetic of DS-5565

Study Design:	
Multicenter, single-arm, open-label study
 
The total study duration will be approximately 16 weeks, consisting of 1-week observation period, 14-week treatment period, and 1-week follow-up period after last dose. After completion of the observation period, the eligible subjects will enter the titration period. For subjects with moderate renal impairment (creatinine clearance [CrCL]: 30-59 mL/min), the titration period will be applied at the first week of 2.5 mg bis in die (BID), and at the second week of 5 mg

	
BID. After the titration period, the drug will be administered for 12 weeks of 7.5 mg BID. For subjects with severe renal impairment (CrCL: 15-29 mL/min), the titration period will be applied at the first week of 2.5 mg quaque die (QD), and at the second week of 5 mg QD. After the titration period, the drug will be administered for 12 weeks of 7.5 mg QD. For subjects with DPNP, any subjects who have been taking prohibited concomitant drugs will undergo a washout period of 7 days or more, prior to the screening. For subjects with PHN, any subjects who have been taking prohibited concomitant drugs or receiving prohibited concomitant therapy will undergo a washout period of 7 days or more, prior to the screening.

Study Duration (from FPI to LPLV):	January 2016 to May 2017
Study Sites and Location:	Approximately 35 study sites in Japan
Planned Sample Size:	Approximately 35 subjects will be enrolled in the study.
Subject Eligibility Criteria:	
Inclusion Criteria:
 
Subjects must satisfy all of the following criteria to be included in the study.
 
For patients with DPNP and patients with PHN:
 

1) Age <math>\geq</math> 20 years at informed consent

2) Able to give written informed consent for study participation, understand procedures of this study, and complete patient-reported questionnaires adequately

3) CrCL (using the Cockcroft-Gault equation): 15-59 mL/min at screening

4) At screening, a pain scale of <math>\geq</math> 40 mm on VAS of SF-MPQ

5) At initiation of study treatment, a pain scale of <math>\geq</math> 40 mm on VAS of SF-MPQ, and completion of at least 4 days of daily pain diaries with an ADPS of <math>\geq</math> 4 over the past 7 days on the 11-point Numerical Rating Scale (NRS)

 
For patients with DPNP only:
 

6) Type 1 or type 2 diabetes mellitus at screening

7) Painful distal symmetric polyneuropathy, diagnosed at least 6 months prior to screening (see Procedures manual for the Diagnosis of Diabetic Peripheral Neuropathy and

Neurological Examination for details)

For patients with PHN only:

- 8) PHN defined as pain present for 3 months or more after herpes zoster skin rash at screening

Exclusion Criteria:

Subjects who meet any of the following criteria will be excluded from participation in the study.

For patients with DPNP and patients with PHN:

- 1) At screening, a pain scale of  $\geq 90$  mm on VAS of SF-MPQ
- 2) At initiation of study treatment, a pain scale of  $\geq 90$  mm on VAS of SF-MPQ, or at least a daily pain score of  $\geq 9$  during observation period
- 3) Major psychiatric disorders at screening or initiation of study treatment
- 4) Use of prohibited concomitant drugs within 7 days prior to screening
- 5) Subjects on hemodialysis, requiring hemodialysis at screening, with acute renal failure, or with a history of kidney transplant.
- 6) Previous administration of pregabalin  $\geq 150$  mg/day for subjects with moderate renal impairment (CrCL: 30-59 mL/min) or  $\geq 75$  mg/day for subjects with severe renal impairment (CrCL: 15-29 mL/min), declared lack of effect
- 7) Previous administration of gabapentin  $\geq 600$  mg/day for subjects with moderate renal impairment (CrCL: 30-59 mL/min) or  $\geq 300$  mg/day for subjects with severe renal impairment (CrCL: 15-29 mL/min), declared lack of effect
- 8) Malignancy other than basal cell carcinoma within the past 2 years prior to screening
- 9) Clinically significant unstable neurologic, ophthalmologic, hepatobiliary, respiratory, hematologic

illness or unstable cardiovascular disease (eg, severe hypotension, uncontrolled cardiac arrhythmia, or myocardial infarction) within 12 months prior to screening

- 10) Clinically significant findings on electrocardiogram (ECG) at screening
- 11) History of pernicious anemia, untreated hypothyroidism, or human immunodeficiency virus infection
- 12) Known history of positive Hepatitis B antigen or Hepatitis C antibody
- 13) Pregnancy, potential pregnancy, breast feeding, or subjects unwilling to take reliable contraceptive measures during the study or for 4 weeks after study completion
- 14) Known hypersensitivity to pregabalin or gabapentin
- 15) Participation in another clinical study, either currently or within 30 days prior to providing of informed consent
- 16) Experience of participating in a DS-5565 clinical study and receiving investigational product
- 17) Abuse of illicit drugs or alcohol within 1 year prior to screening
- 18) Response of “yes” to any of the questions in the Columbia-Suicide Severity Rating Scale (C-SSRS) at screening or initiation of study treatment in relation to events occurring within the past 12 months
- 19) Previous treatment with drugs that could cause irreversible retinal degeneration
- 20) At screening, clinical laboratory values exceeding limits listed in Table 4-1 (see Section 4.1.3)
- 21) Subjects who are considered inappropriate for the study at the discretion of the investigator or sub-investigator

For patients with DPNP only:

- 22) Hemoglobin A1c (National Glycohemoglobin Standardization Program) > 10.0% at screening

---

- 23) Uncontrolled blood glucose at screening at initiation of study treatment that may require changes in diabetes treatment (non-insulin drug therapy, exercise therapy, diet therapy) during the study
- 24) Other severe pain at screening or initiation of study treatment, unrelated to diabetic peripheral neuropathy (DPN), that may confound the assessment of DPNP
- 25) Neurologic disorders at screening or initiation of study treatment, unrelated to DPN, that may confound the assessment of DPNP
- 26) Skin conditions that may confound the assessment of DPNP
- 27) Amputation of lower limb parts, other than toes, prior to screening or initiation of study treatment
- 28) Change of restricted concomitant drugs for patients with DPNP within 30 days prior to screening

For patients with PHN only:

- 29) Previous use of neurolytic block (eg, chemical neurolytic block using phenol or ethyl alcohol, radiofrequency thermocoagulation) or neurosurgical therapy for current PHN
- 30) Other severe pain at screening or initiation of study treatment, unrelated to PHN, that may confound the assessment of PHN
- 31) Neurologic disorders at screening or initiation of study treatment, unrelated to PHN, that may confound the assessment of PHN
- 32) Skin conditions that may confound the assessment of PHN
- 33) Change of restricted concomitant drugs for patients with PHN within 14 days prior to screening
- 34) Use of prohibited concomitant therapies within 7 days prior to screening
- 35) Known immunocompromised status (eg, systemic lupus

---

	
erythematosus, acquired immune deficiency syndrome, patients receiving immunosuppressants due to autoimmune disorder)
 
For patients with DPNP and patients with PHN:
 
36) Response of “yes” to the suicidality question (current or past) on the Major Depressive Episode Module (Module A) or response of “yes” to any question of B1b, B3 through B11c, B13, or B14 in the Suicidality Module (Module B) on the Mini-international Neuropsychiatric Interview (MINI) (Version 6.0) Interview at screening


Dosage Form, Dose, and Route of Administration:
	
For subjects with moderate renal impairment at screening (CrCL: 30-59 mL/min): For the fixed dose period, DS-5565 at a total daily dose of 15 mg (7.5 mg BID), formulated in 2.5 mg and 5 mg tablets, will be administered orally twice daily (in the morning and at bedtime). For the titration period, DS-5565 will be administered with 5 mg (2.5 mg BID) during the first week, and followed by 10 mg (5 mg BID) during the second week.
 
For subjects with severe renal impairment at screening (CrCL: 15-29 mL/min): For the fixed dose period, DS-5565 at a total daily dose of 7.5 mg (7.5 mg QD), formulated in 2.5 mg and 5 mg tablets, will be administered orally once daily (at bedtime). For the titration period, DS-5565 will be administered with 2.5 mg (2.5 mg QD) during the first week, and followed by 5 mg (5 mg QD) during the second week.

Study Endpoints:
	
Primary endpoint: The safety and tolerability of DS-5565 in subjects with moderate to severe renal impairment
 
Secondary endpoints:
 
 
• Change in ADPS from baseline to Week 14
 
• ADPS Responder rate defined as the proportion of subjects with <math>\geq 30\%</math> and <math>\geq 50\%</math> reduction from baseline to Week 14
 
• Change from baseline in parameters assessed using SF-MPQ including 15 pain descriptors (ranked on 4-stage intensity scale), the Present Pain Intensity index
 

	
(ranked on a 6-stage intensity scale), and VAS (100-mm scale)
 

• Patient Global Impression of Change assessed on a 7-point scale (from very much improved to very much worse)

• Change from baseline in average daily sleep-interference score

Statistical Analyses:	
For the safety endpoints, AEs, clinical laboratory test results, vital sign, ECG, physical findings (including body weight), C-SSRS, HADS, etc will be summarized by CrCL group using the safety analysis set. Quantitative data will be tabulated with descriptive summary statistics. For categorical data, frequency tables will be provided.
 
All efficacy endpoints will be analyzed using the safety analysis set. Observed weekly ADPS and change from baseline will be summarized by CrCL group and week.
 
Missing weekly ADPS values will be imputed based on a multiple imputation method using “nonfuture dependence” model which is specified by the pattern mixture approach with shifting parameters under missing not at random mechanism. Each complete imputed dataset will be analyzed using the repeated measures analysis and Rubin’s rule will be used to combine the results.

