### **2.2 Study Hypothesis**

The primary hypothesis of this open-label study is that DS-5565 will be generally safe and well-tolerated when the drug is administered with a dosing of 7.5 mg BID in subjects with moderate renal impairment (Creatinine Clearance [CrCL]: 30-59 mL/min) and 7.5 mg QD in subjects with severe renal impairment (CrCL: 15-29 mL/min).

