## **3.2 Discussion of Study Design**

### **3.2.1 Dosage of DS-5565**

Dose regimens were selected based on results of single-dose studies in subjects with renal impairment volunteers, as well as modeling and simulation. Study DS5565-A-J115 was conducted to assess pharmacokinetics (PK) of DS-5565 in Japanese subjects with renal impairment. As the result of DS5565-A-J115, no notable differences were found in  $C_{max}$  among the subjects with normal, mild, and moderate renal impairment.

However, the  $C_{max}$  was higher in the subjects with severe renal impairment. The geometric LS mean ratio of  $C_{max}$  in comparison to the subjects with normal renal function was 1.5 for the subjects with severe renal impairment. The  $AUC_{last}$  increased with severity of renal impairment: the  $AUC_{last}$  was 1.3 times higher for the subjects with mild renal impairment, 1.9 times higher for moderate renal impairment, 3.6 times higher for severe renal impairment. These results were similar to the results of Study DS5565-A-E106, which was conducted to assess PK of DS-5565 in Western subjects with renal impairment. Population PK analysis was conducted for Study DS5565-A-E106 to evaluate the effect of CrCL on DS-5565 exposure. The treatment groups were analyzed by normal CrCL ( $\geq 90$  mL/min), mild reduction in CrCL (60 to 89 mL/min), moderate reduction in CrCL (30 to 59 mL/min), and severe reduction in CrCL (15 to 29 mL/min). Relative to subjects with normal renal function, total clearance of

DS-5565 was predicted about 11%, 56%, and 73% lower than in subjects with mild, moderate, and severe renal impairment, respectively. Based on these results, a half dose in subjects with moderate renal impairment and a quarter dose in subjects with severe renal impairment are expected to be equivalent exposure to a dose in subjects with normal renal function. A BID doses of 15 mg was selected as a maximum dosing regimen in Phase 3 studies (DS5565-A-J303, DS5565-A-J304), therefore BID doses of 7.5 mg and QD doses of 7.5 mg in subjects with moderate and severe renal dysfunction, respectively are expected to produce exposures equivalent to a BID doses of 15 mg in subjects with normal renal function (Table 3-1).

Along with on-going Phase 3 studies (DS5565-A-J303, DS5565-A-J304), the duration of the titration period of this study is 2 weeks.

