Table 3-1 Predicted DS-5565 AUC and  $C_{max}$  with Once Daily and Twice Daily Doses of 7.5-15 mg in Subjects with Renal Dysfunction (Estimation from DS5565-A-E106)

CrCL Group (mL/min)	Dose	$AUC_{ss,0-24h}$ (ng*h/mL)		$C_{max,ss}$ (ng/mL)	
		Mean	Median (min, max)	Mean	Median (min, max)
≥ 90	15 mg BID	1720	1616 (1311, 2806)	226	233 (176, 281)
60-89	15 mg BID	1899	1823 (1536, 2281)	239	226 (162, 327)
30-59	7.5 mg BID	1741	1850 (1345, 2080)	163	161 (119, 209)
15-29	7.5 mg QD	1529	1488 (1260, 1958)	152	156 (118, 177)

AUC = area under the plasma concentration-time curve;  $AUC_{ss,0-24h}$  = area under the plasma concentration-time curve at steady state from 0 to 24 hours;  $C_{max,ss}$  = maximum plasma concentration at steady state; CrCL = creatinine clearance; BID = twice daily; QD = once daily

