#### 4.2 Subject Withdrawal

Data from all medicated subjects are important to achieve study objectives, and subjects should be encouraged to adhere to protocol instructions and visit schedules. However, in accordance with the Declaration of Helsinki and other applicable regulations, a subject has the right to withdraw from the study at any time and for any reason without prejudice to his or her future medical care by the study physician or at the study site. The

investigator is also free to terminate a subject's involvement in the study at any time if the subject's clinical condition warrants such action. The sponsor or regulatory authorities also may request termination of the study at any time due to safety issues or concerns related to study conduct.

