#### **4.2.1 Withdrawal Criteria**

If a subject meets the following withdrawal criteria, that subject should be withdrawn from the study.

- Difficulty of continuing the study due to AE
- Subjects with any of the following elevations in clinical laboratory values
  - Increase in ALT or AST  $\geq 5 \times$  ULN
  - ALT or AST rises to  $\geq 3 \times$  ULN and persists for more than 2 weeks
  - Concurrent increases in ALT or AST  $\geq 3 \times$  ULN and total bilirubin (T-Bil)  $\geq 2 \times$  ULN
  - ALT or AST  $\geq 3 \times$  ULN associated with a clinical presentation suggestive of liver injury (ie, including the appearance of fatigue, nausea, vomiting, jaundice, right upper quadrant pain or tenderness, fever, rash, and/or eosinophilia)
- Decrease in CrCL  $< 15$  mL/min
- AE related to suicide (if there are any "yes" responses to any of the questions in the C-SSRS)
- Withdrawal by subject (ie, withdrawal of consent)
- Major deviation from study procedure

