#### **4.2.2 Reasons for Withdrawal**

If a subject discontinues from the study treatment for any reason, the date and the reason for discontinuation must be recorded in the Electronic Case Report Form (eCRF) using the following criteria.

For subjects withdrawn prior to randomization but after signing informed consent

- Screen failure
- Withdrawal by subject (eg, AE, Lack of efficacy [LOE], Other)
- Physician decision
- Other

For subjects withdrawn after the initiation of study treatment but before completing the study as per protocol

- AE
- Death
- LOE
- Lost to follow-up
- Protocol violation
- Decrease in CrCL < 15 mL/min
- Pregnancy
- Study terminated by sponsor
- Withdrawal by subject (eg, AE, LOE, Other)
- Other

If a subject is withdrawn due to need for a prohibited medication, the reason may be recorded as LOE, as appropriate. Reasons recorded under “Protocol violation” may include failure to comply with protocol requirements or study procedures.

For all subjects who withdraw from the study, the investigator must complete and report pertinent observations as thoroughly as possible up to the date of withdrawal, including the date of last treatment and the reason for withdrawal.

If a subject is withdrawn due to an AE, the investigator should follow the subject until the AE has resolved or stabilized.

All subjects who are withdrawn from the study should complete protocol-specified withdrawal procedures (see Section 4.2.3 and Section 6.4).

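### Dose follows screening CrCL and the only on-treatment renal rule is withdrawal below 15 mL/min, so a moderate-group subject who falls into 15-29 stays by default on twice the dose assigned to that range

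*Combined protocol and SAP*

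**What the plan says.** **Dose assignment.** The Synopsis ties the regimen to renal function at one time point: "moderate renal impairment at screening (CrCL: 30-59 mL/min): For the fixed dose period, DS-5565 at a total daily dose of 15 mg". Section 5.1.2 and Table 5-1 run that regimen, after two weeks of titration, to Day 98 or 99. Neither has a rule for changing it when renal function changes.

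**Renal rule on treatment.** Section 4.2.1 opens with "If a subject meets the following withdrawal criteria, that subject should be withdrawn from the study". The one renal item on its list, repeated as a withdrawal reason in Section 4.2.2, is "Decrease in CrCL < 15 mL/min". It is the same for both dose groups.

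**Dose intended for CrCL 15-29.** Section 2.2 frames the hypothesis for "7.5 mg QD in subjects with severe renal impairment (CrCL: 15-29 mL/min"). Section 3.2.1 gives the reasoning. From population PK, total clearance of "DS-5565 was predicted about 11%, 56%, and 73% lower than in subjects with mild, moderate, and severe renal impairment, respectively", evidently meant as reductions from normal function. AUC in the Japanese renal study was "1.9 times higher for moderate renal impairment, 3.6 times higher for severe renal impairment". Table 3-1 gives predicted exposure "with Once Daily and Twice Daily Doses of 7.5-15 mg in Subjects with Renal Dysfunction (Estimation from DS5565-A-E106"). The stated aim is exposure equivalent to 15 mg BID in normal function.

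**Discretionary safeguards.** Under Section 4.2 the investigator may end participation if the subject's "clinical condition warrants such action". Tolerability is reviewed before each dispensing (6.3.1, 6.3.2), subjects may be withdrawn for AEs (4.2.1), clinically significant laboratory changes count as AEs (9.4), and a DSMB reviews safety (11.9). Table 9-1 has a dose-reduced category for recording, but Section 5 does not say when a reduction is allowed or to what dose. Section 5.1 requires the product to be used only as the protocol directs.

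**The concern.** This drug is cleared almost entirely by the kidney: Section 1.1.1.5.1 reports 96.85% of radioactivity recovered in urine, and Section 1.2 says exposure depends on renal function. The dose is halved or quartered for that reason. Yet the rule that sets dose looks at CrCL once, and the next written rule acts only at 15 mL/min. Between 29 and 15, a subject who entered as moderate receives double the dose that the protocol's own rationale gives to someone with the same CrCL who entered as severe.

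Safety and tolerability are the primary objective. With about 35 subjects, one subject's event is at least 1/35 = 2.9 percentage points of the pooled column, and more of the moderate column. An event at a dose not meant for that renal function would count against the 15 mg/day regimen. PK sampling ends at Visit 6 (Week 6), so a later fall would leave no concentration data.

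**Working it through.** **Inputs.** Table 3-1 mean AUCss,0-24h (ng·h/mL): 1720 for CrCL ≥90 on 30 mg/day; 1741 for 30-59 on 15 mg/day; 1529 for 15-29 on 7.5 mg/day. The largest AUC in the table is 2806, in the normal-function row. Section 3.2.1: clearance reductions of 56% and 73%; AUC ratios of 1.9 and 3.6.

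**1. The plan's own equivalence.** 1741/1720 = 1.01 and 1529/1720 = 0.89, so the assigned doses do give roughly normal-function exposure. With CL/F = daily dose / AUC:
- normal: 30000/1720 = 17.44 L/h
- moderate: 15000/1741 = 8.616 L/h, 50.6% below normal
- severe: 7500/1529 = 4.905 L/h, 71.9% below normal

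This is close to the stated 56% and 73%.

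**2. A typical CrCL 15-29 subject left on 15 mg/day**, assuming AUC proportional to dose:

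| Basis | AUC | Multiple of 1720 |
|---|---|---|
| Table 3-1 severe mean, doubled: 2 × 1529 | 3058 | 1.78 |
| Clearance reductions: 1741 × 0.44/0.27 | 2837 | 1.65 |
| AUC ratios: 1741 × 3.6/1.9 | 3299 | 1.92 |

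Doubling the severe row's individual range (1260 to 1958) gives 2520 to 3916, so some subjects would remain below 2806.

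**3. Where AUC passes 2806.** This requires CL/F = 15000/2806 = 5.346 L/h. The documents give no function linking CrCL to AUC, so the answer depends on the interpolation. Placing the Table 3-1 means at assumed band midpoints of 44.5 and 22 mL/min gives a slope of (8.616 − 4.905)/22.5 = 0.165 L/h per mL/min. The crossing is then 22 + (5.346 − 4.905)/0.165 = 24.7.

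| Method | CrCL at crossing |
|---|---|
| Table 3-1 means | 24.7 |
| Table 3-1 medians | 24.2 |
| 1.9 and 3.6 ratios | 24.6 |
| 56% and 73% reductions | 26.8 |
| 2-fold and 4-fold ratios (Section 1.1.1.5.2) | 27.1 |
| Proportional to CrCL, from severe / moderate row | 24.0 / 27.6 |
| Straight line through all four groups, normal group at 110 to 90 | 20.3 to 25.0 |

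On the first method AUC is 2475 at CrCL 29, 2778 at 25, 3058 at 22 and 3278 at 20. Just below 30 it may therefore stay inside the table.

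**4. Cmax.** Doubling the severe-row mean gives at most 2 × 152 = 304 ng/mL, below the table maximum of 327. Doubling that row's individual maximum gives an upper bound of 2 × 177 = 354, above it. Individual exceedance is neither shown nor excluded.

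**5. The opposite error.** On the first method CL/F at CrCL 30 is 4.905 + 8 × 0.165 = 6.22 L/h, so 7.5 mg/day gives 7500/6.22, about 1205. That is below the lowest AUC in Table 3-1 (1260). Switching a subject on a noisy reading would under-dose.

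**6. Noise alone.** This was simulated with assumed inputs: no true decline, within-subject CV 6-12%, subjects screened at 30-59, nine later readings. With underlying CrCL uniform on 20-75, a CrCL below 30 confirmed on repeat occurs in 5-10% of moderate subjects; 52-59% of those truly have CrCL ≥30. Repeat tests number 0.3-0.6 per moderate subject. With uniform 20-50 the figures are 7-15% and 0.46-0.93.

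**The case against.** The strongest reply is that the gap may rarely matter. Acute renal failure is excluded at entry. Falling from mid-band 44.5 to 25 would mean losing about 44% of CrCL within 14 weeks. Creatinine is measured at every visit, so a large fall would be seen, and the investigator, the AE rules and the DSMB can all act. Section 15.5 also permits an immediate deviation to remove an apparent immediate hazard.

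Much of this stands. The frequency of true falls cannot be derived from the documents. What does not stand is that discretion fills the gap: no safeguard ties dose to CrCL, several act mainly after a problem shows, and none names a permitted lower dose. Given Section 5.1, an investigator who sees CrCL 21 in a subject without symptoms has no protocol-defined step except ending participation.

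Three stronger readings are tempting, and the documents do not support them.
- A reader might take 2806 as a safety ceiling. It is the largest estimate in one table, drawn from one study, and it belongs to a subject with normal function. The protocol does not use it as a limit and nothing shows harm above it.
- A reader might want a mandatory dose cut at a fixed CrCL such as 25. That cut-off would rest on an interpolation spanning 20 to 28.
- A reader might infer that an analysis has been left out. Section 11.2 defers detailed methods to a separate SAP that is not in the text reviewed, so no omission is claimed.

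A mid-study dose change would also blur a hypothesis framed by fixed regimen (Section 2.2). That is fair, and is why the fix offers withdrawal as an alternative and flags any reduced dose.

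**Conclusion.** The point holds as a minor safety improvement. Confidence is high that the text has the gap: dose is set at screening, the only renal rule on treatment is CrCL below 15, and a moderate-group subject who truly falls into 15-29 stays by default on double the dose assigned to that range. Confidence is low on the size of the consequence. For a typical such subject, predicted AUC is about 3058 ng·h/mL, or 1.65 to 1.92 times the normal-function mean. This rests on dose proportionality and on band averages standing for individuals. No claim is made about clinical harm, about Cmax, or about how many subjects would be affected.

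**What to change.** **Dosing rule (Sections 4.2.1 and 5.1.2).** For moderate-group subjects, a CrCL below 30 mL/min confirmed on a repeat sample requires a documented investigator review as soon as the result is known, and no later than the next dispensing. At that review the protocol expressly permits either dropping the morning dose or withdrawal. The bedtime combinations in Tables 5-2 and 5-3 are the same in every week (2.5; 5; 2.5 + 5 mg), so dropping the morning dose gives exactly the severe-group regimen without new supplies. The switch should not be automatic.

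**Reporting (Section 11.7).** Derive Cockcroft-Gault CrCL at each visit from creatinine (Table 9-2) and weight (Section 9.7.1), both already collected. List TEAEs with the actual daily dose and latest CrCL at onset. Keep the main tables by screening CrCL group and flag any subject whose dose was reduced.

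**Cost.** Protocol wording, one derived variable, one listing and some repeat creatinine tests. If all 35 subjects were moderate, noise alone would cause about 0.3 × 35 = 11 to 0.93 × 35 = 33 repeats across the two assumed CrCL distributions. About half of confirmed results below 30 may come from subjects whose true CrCL is 30 or above, which is why they prompt review only. A few subjects may contribute 7.5 mg/day exposure to the 15 mg/day column; the flag makes this visible.
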